- We will also conduct secondary analyses with PrEP adherence measured as continuous TFV-DP levels and will conduct descriptive summaries of PrEP adherence measured as a five-category variable: BLQ, BLQ-349 fmol/punch, 350-699 fmol/punch, 700-1249 fmol/punch, and ≥ 1250 fmol/punch.

Predictor(s) of interest: Randomized arm (SMS vs. WhatsApp groups; drug level feedback counseling vs. monthly counseling)

Statistical analysis: We will assess the short-term and long-term effects of the intervention on PrEP adherence using the same methods as described for the primary outcome (primary analyses 1 and 2). Shorter term efficacy will be estimated by comparing month 2 TFV-DP levels between primary randomization groups. Longer term efficacy will be estimated by comparing month 12 TFV-DP levels between primary randomization groups and also between secondary randomization groups, among non-responders to the first-line intervention.

Secondary Analysis 2: Create models to estimate the probability of adherence based on sociodemographic factors, individual- and partner-level characteristics, risk practices, and study arm.

Analysis population: All enrolled study participants

Outcome: PrEP adherence the 9-month study visit, defined as a binary outcome variable around TFV-DP levels of 700 fmol/punch

Predictor(s) of interest: Demographics (e.g., age, education), sexual behavior, sexually transmitted infections, perceived risk of HIV, HIV-related stigma, self-efficacy to use PrEP, relationship power dynamics, transactional sex, intimate partner violence, depression, traumatic stress symptoms, alcohol use, treatment arm.

Statistical analyses:

- 1) We will construct risk prediction tools to estimate the probability of adherence at 9 months based on the predictors listed above. We will fit Poisson regression models with all predictors of interest and binary 9-month adherence (TFV-DP ≥ 700 fmol/punch) as the outcome. We will construct two risk prediction tools:
 - i. **Baseline tool:** this model will include all participants, and so will be applicable to the population of AGYW in South Africa. Here, the treatment arm variable will simply be an indicator of SMS/WhatsApp. All predictors will be measured at baseline.

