 - ii. **Non-responder tool:** this model will include those individuals who did not respond to first-line treatment, so it will be generalizable to this subgroup of the population. In this model, the treatment arm variable will be an indicator of DLFB/enhanced counseling. We will also include first-line

treatment. This model will use the most recent values of the predictors of interest (i.e., the most recent available at the time of rerandomization).

- 2) We will evaluate model performance by estimating the area under the receiver operating characteristic curve (AUC) and the calibration intercept and slope. These measures will be adjusted for resubstitution bias via the bootstrap (see Harrell, *Regression Modeling Strategies*).
- 3) There is very little missingness of predictors of interest at baseline. Thus, the first model ("baseline tool") will be based on a complete case analysis, and the second model ("non-responder tool") will be based on last observation carried forward for participants with baseline data available; those without baseline data will be excluded.

Code for risk prediction model fitting and performance assessment

```
library(rms)

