## Simulate data with 200 observations, 3 predictors (x1, x2, x3), and
outcome y
set.seed(17)
x1 <- rnorm(200, 0, 1)
x2 <- rnorm(200, 1, 1)
x3 <- rnorm(200, -1, 1)
lp <- -2 + 0.5*x1 + 1*x2 - 0.5*x3
expit <- function(x) exp(x)/(1+exp(x))
y <- rbinom(200, 1, expit(lp))

fit <- lrm(y ~ x1 + x2 + x3, x=TRUE, y=TRUE) ## fit prediction model with 3
predictors (logistic regression model)
pentrace.fit <- pentrace(fit, seq(0, 100, by=0.5)) ## search for best
penalty
fit.penal <- update(fit, penalty = pentrace.fit$penalty) ## update model
with best penalty to get penalized model

set.seed(29)
validation_rslt <- validate(fit.penal, bw=F, B=1000, Dxy.method="somers2")

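### The SAP's risk-prediction text specifies unpenalised Poisson regression, but its fitting code uses penalised logistic regression; the text version can give predicted probabilities above 1

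*SAP*

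**What the plan says.** SAP Secondary Analysis 2, Statistical analyses item 1, gives the purpose: "We will construct risk prediction tools to estimate the probability of adherence at 9 months based on the predictors listed above". The same item names the model: "We will fit Poisson regression models with all predictors of interest and binary 9-month adherence". It describes a baseline tool for all participants and a tool for non-responders to first-line treatment. No penalty or other shrinkage is mentioned.

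Item 2 of the same section says performance will be judged by "estimating the area under the receiver operating characteristic curve (AUC) and the calibration intercept and slope", with a bootstrap correction for resubstitution bias.

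A code block follows, headed "Code for risk prediction model fitting and performance assessment". It differs from item 1 at three steps:

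- The fit is `lrm`: "fit <- lrm(y ~ x1 + x2 + x3, x=TRUE, y=TRUE". The comment beside it reads "predictors (logistic regression model".
- A penalty is searched from 0 to 100 in steps of 0.5 and then applied: "fit.penal <- update(fit, penalty = pentrace.fit$penalty".
- The penalised logistic fit is what gets validated: "validation_rslt <- validate(fit.penal, bw=F, B=1000". The AUC and the calibration intercept and slope are read from that result.

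Protocol section 6.4.2 names logistic regression for the correlates of adherence at months 2 and 9. That agrees with the code rather than with the SAP text.

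**The concern.** Two analysts could follow the same SAP section and produce different tools. They would differ in link function, in whether coefficients are shrunk, and in what the calibration intercept and slope refer to.

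The choice matters because the product is an individual probability. Poisson regression with a log link and robust errors is a sound way to estimate a relative risk between arms. As a prediction model for a binary outcome it has no upper bound at 1, and the SAP has no rule for values beyond it. The code's calibration measures come from a logistic fit, so they would not describe a Poisson tool.

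The missing penalty is a separate gap. The non-responder tool has many predictors for its size, and the text drops the step that the code uses to limit overfitting.

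**Working it through.** The documents give no sample size, event count or expected performance for Secondary Analysis 2, so there is no planned figure to reproduce. The contradiction itself needs no arithmetic. The checks below size its consequences.

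**1. The SAP's seeded example.** Inputs from the code block: seed 17, n=200, three predictors with means 0, 1 and -1 and SD 1, true logit = -2 + 0.5·x1 + 1·x2 - 0.5·x3. Both models were fitted to those 200 records, the logistic one without its penalty:

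- Poisson: log p = -2.158 + 0.336·x1 + 0.531·x2 - 0.307·x3. Largest fitted value 1.66; 5 of 200 (2.5%) above 1.
- Logistic: logit p = -2.561 + 0.618·x1 + 1.060·x2 - 0.590·x3. Largest fitted value 0.936.

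To see the mechanism, take a woman with x1=1, x2=3, x3=-2.

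- Poisson: -2.158 + 0.336 + 1.593 + 0.613 = 0.385, and exp(0.385) = 1.47.
- Logistic: -2.561 + 0.618 + 3.180 + 1.180 = 2.417, which gives 0.918.
- True value: -2 + 0.5 + 3 + 1 = 2.5, which gives 0.924.

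**2. Repeated draws from the same example.** At n=200, 99.4% to 99.6% of data sets (separate runs of 500 and 1,000) had at least one Poisson prediction above 1. The median maximum was 1.62 to 1.63, and 3.2% to 3.3% of records were above 1 on average. Average AUC is the same under both models (0.781).

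**3. Closer to the trial.** Sizes: about 350 women for the baseline tool (SAP, Study Design) and 166 non-responders (Protocol 6.3). The predictor list in Secondary Analysis 2 has 13 entries, counting treatment arm. Adherence level, signal strength and independent normal predictors are assumptions. Signal is the SD of the true linear predictor. Each cell shows the share of 300 simulated data sets with any Poisson prediction above 1:

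| Adherence | n=350, SD 0 | n=350, SD 0.5 | n=350, SD 1 | n=166, SD 0 | n=166, SD 0.5 | n=166, SD 1 |
|---|---|---|---|---|---|---|
| 10% | 0.7% | 5.3% | 51.3% | 7.3% | 16.0% | 50.7% |
| 25% | 0.7% | 25.0% | 96.3% | 15.7% | 36.7% | 90.3% |
| 40% | 3.7% | 64.3% | 99.7% | 29.3% | 70.0% | 98.3% |

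At n=350, 40% adherence and SD 0.5, an average of 0.4% of women were above 1; at SD 1 it was 2.6%. No logistic prediction exceeded 1 in any cell, as the link guarantees.

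**4. Shrinkage in the non-responder tool.** This tool adds first-line treatment, so it has at least 13 + 1 = 14 predictors (demographics covers more than one variable). Protocol 6.3 plans on 149 to 184 non-responders, counting its text and Table 2, with 25% to 50% adherence by arm. Averaging the two arms within each Table 2 scenario gives 32.5% or 40%.

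- Low end: 149 × 0.325 = 48 events; 48.4 / 14 = 3.5 per predictor.
- High end: 184 × 0.40 = 74 events; 73.6 / 14 = 5.3 per predictor.

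In a simulation with n=166, 14 independent normal predictors and about 35% adherence, unpenalised Poisson had a median out-of-sample calibration slope of about 0.38 at SD 0.5 and 0.65 at SD 1. The ideal is 1. An unpenalised logistic fit would be overfitted too, so this point concerns the missing penalty and not the link.

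**The case against.** The strongest reply is that the harm depends on facts not yet known. A reader might infer that the text version is bound to give impossible probabilities in this trial. The documents do not support that. They give neither 9-month adherence nor predictor strength for this model, and with low adherence or weak predictors a value above 1 would be rare. The 99% figure comes from strongly separated toy data written to show syntax, so it is illustrative. Counting data sets with at least one such value also sounds worse than the share of women affected. All of this stands.

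A reader might also infer that the text leaves the tools with no protection against overfitting. That goes too far. Item 2 corrects AUC, calibration intercept and slope by bootstrap, so overfitting would show in the reported performance. The correction does not shrink the coefficients that a user of the tool would apply.

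Two further replies are weaker. One is that the code is only an example. Its data are simulated, but its heading and comments present it as the fitting and assessment procedure, and it is the only place that shows how the calibration measures are obtained. The other is that modified Poisson is used in Primary Analyses 1 and 2. There it estimates relative risks, which is a different purpose and is not questioned here. It may explain how the word entered this section, but the documents do not say which model was intended.

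**Conclusion.** The point holds as an internal contradiction in SAP Secondary Analysis 2, over both the model and the penalty. That part is certain from the documents alone.

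The consequence is conditional. The text version can give probabilities above 1. With 13 predictors and n=350 the chance of at least one runs from about 1% to nearly 100% of data sets over assumed adherence of 10% to 40% and null to strong signal. It is about 64% at 40% adherence with moderate signal. These figures rest on independent normal predictors and assumed signal strengths.

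The damage is confined to predicted probabilities and calibration; AUC is practically the same under either model. Leaving out the penalty matters most for the non-responder tool. This is a secondary analysis: the primary endpoint, the randomised comparisons and safety are not affected. It should be corrected before the models are fitted.

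**What to change.** Change the model sentence in Secondary Analysis 2, item 1, to penalised logistic regression with the penalty chosen as in the code, for both the baseline and the non-responder tool. Text, code and calibration measures then describe one model, and the choice agrees with Protocol section 6.4.2. The cost is one SAP sentence, since the code exists.

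If Poisson is kept on purpose, the SAP needs matching fitting and validation code, a stated shrinkage method, and a rule for predictions above 1.

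Repeating the penalty search inside each bootstrap resample, so that the optimism correction covers it, is an optional refinement and not part of this defect.

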## Simulate data with 200 observations, 3 predictors (x1, x2, x3), and
outcome y
set.seed(17)
x1 <- rnorm(200, 0, 1)
x2 <- rnorm(200, 1, 1)
x3 <- rnorm(200, -1, 1)
lp <- -2 + 0.5*x1 + 1*x2 - 0.5*x3
expit <- function(x) exp(x)/(1+exp(x))
y <- rbinom(200, 1, expit(lp))

fit <- lrm(y ~ x1 + x2 + x3, x=TRUE, y=TRUE) ## fit prediction model with 3
predictors (logistic regression model)
pentrace.fit <- pentrace(fit, seq(0, 100, by=0.5)) ## search for best
penalty
fit.penal <- update(fit, penalty = pentrace.fit$penalty) ## update model
with best penalty to get penalized model

set.seed(29)
validation_rslt <- validate(fit.penal, bw=F, B=1000, Dxy.method="somers2")

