6.3. Accrual, Follow-up, and Sample Size

For the SMART trial design, the goal is to enroll and randomize up to 500 women in order to achieve an analysis sample size of approximately 350 women who return for their one-month study visit and will want to continue PrEP for a further 9 months: 175 per arm randomized into the first intervention at enrollment, continuing past their 1-month study visit and evaluable at 9 months. Up to 500 women who initiate PrEP will be enrolled over a period of approximately 18 months. 350 evaluable women

would have 96% power for the initial randomization to detect an increase from 40% response at 2 months to SOC + two-way SMS to 60% with the SOC + WhatsApp groups. Among the estimated 70-105 non-responders in each initial group, we have 79-96% power in each group of non-responders to detect a 30% difference in adherence at 9 months between women randomized to monthly counseling or drug level feedback. Pooling across the initial randomization, with 149-166 women we would have ~80% power to detect ~ 15-20% difference (Table 2).

Table 2: Power to assess differences in adherence by intervention strategies in each of the first and second stages using a one-sided $\alpha = 0.025$.

First Randomization			Second randomization (Pooled across first randomization)			
% Adherent				% Adherent		
WhatsApp + SOC N = 175	SMS + SOC N = 175	Power	Non-responders Total N	Monthly visits	Drug Level Counseling	Power
65%	40%	99%	166	40%	25%	84%
				50%	30%	89%
60%	40%	96%	175	40%	25%	86%
				50%	30%	91%
55%	40%	84%	184	40%	25%	88%
				50%	30%	91%

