## validate penalized model
validation_rslt[3,5] ## calibration intercept
validation_rslt[4,5] ## calibration slope
validation_rslt[1,5]/2 + 0.5 ## AUC
```

Secondary Analysis 3: Assess the degree of prevention-effective adherence and factors associated with prevention-effective adherence.

Analysis population: All enrolled study participants

Outcome: Prevention-effective adherence

Predictor(s) of interest: Demographics (e.g., age, education), sexual behavior, sexually transmitted infections, perceived risk of HIV, HIV-related stigma, self-efficacy to use PrEP, relationship power dynamics, transactional sex, intimate partner violence, reported side effects, social harms, serious adverse events, depression, traumatic stress symptoms, alcohol use

Statistical analyses: The planning for this analysis is in the preliminary stages. The SAP will be updated with more details when available.

Secondary Analysis 4: Characterize SMS response rates and the content and frequency of use of WhatsApp groups.

Analysis population: All enrolled study participants in either the SMS or WhatsApp groups (will assess outcomes separately for each group)

Outcome: SMS response rates, WhatsApp group engagement

Statistical analyses:

- 1) We will compute descriptive statistics to summarize the engagement in SMS messaging and WhatsApp groups over time in the study, defined as follows:
 - a. Level of engagement in SMS intervention: 1 = successful completion of an SMS contact in a given week, defined as either successful response of “yes” to an SMS message or a successful phone call attempt after either a “no” response or the first non-response after a prior response. 0 = an unsuccessful phone call attempt after a “no” or first non-response in a given week or participant removed themselves from the SMS messages.
 - b. Level of engagement in WhatsApp groups: 1 = enrolled in a WhatsApp group for a given week; 0 = removed from a WhatsApp group in a given week.
- 2) We will also compute descriptive statistics to describe the total number of SMS and WhatsApp messages sent on average each week, the number of participants responding to the WhatsApp messages during a given week, and any differences in WhatsApp activity by group number (e.g., WhatsApp group 1 versus WhatsApp group 2).

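### SAP Secondary Analysis 2: the template code tunes the penalty once, outside the bootstrap, so the corrected calibration slope omits that step and tends to run high when signal is weak and predictors are many

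*SAP*

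**What the plan says.** SAP Secondary Analysis 2 plans two prediction tools for month-9 adherence: one for all participants and one for non-responders to first-line treatment. Item 2 names three performance measures (AUC, calibration intercept, calibration slope) and states: "These measures will be adjusted for resubstitution bias via the bootstrap".

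The code that follows works on simulated data with 200 observations and 3 predictors. In order, it:

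1. fits a logistic model;
2. searches for a penalty on the full-data fit, "pentrace.fit <- pentrace(fit, seq(0, 100, by=0.5";
3. carries the single chosen value into the final model, "fit.penal <- update(fit, penalty = pentrace.fit$penalty";
4. calls `validate()` on that penalized fit with B=1000;
5. reads off the corrected measures, among them "validation_rslt[4,5] ## calibration slope".

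No penalty search occurs between steps 4 and 5. Item 1 of the text specifies Poisson regression and does not mention a penalty. Penalization appears only in the code.

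**The concern.** A bootstrap corrects for the modelling steps that it repeats. Here the penalty is chosen from the data, but every bootstrap refit inherits the full-data choice. When signal is weak, that choice is a heavy penalty. Each refit is then strongly shrunk and is scored on the original sample, which shares many women with the resample. Scored on those women, the predictions look too narrow, and the slope comes out above 1 for that reason.

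At stake is one of the three stated performance measures of a secondary analysis. A slope well above 1 describes a tool whose predictions vary too little. If the true slope is near 1, that description is wrong. No treatment comparison is affected.

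**Working it through.** The documents state no calibration slope, so there is no figure to reproduce. The check is a simulation of the coded sequence.

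**Inputs**
- Non-responders: Protocol 6.3 gives several figures. Its text says "Pooling across the initial randomization, with 149-166 women we would have ~80% power"; Table 2 has 166-184; 70-105 per initial arm gives 2 × 70 = 140 to 2 × 105 = 210. Base case 175, the middle row of Table 2.
- Month-9 adherence in non-responders: Table 2 arm averages are (40 + 25)/2 = 32.5% and (50 + 30)/2 = 40%. Base case 33%, so 175 × 0.33 ≈ 58 adherent women.
- Predictors: the SAP list starts "Demographics (e.g., age, education), sexual behavior, sexually transmitted infections, perceived risk of HIV, HIV-related stigma, self-efficacy to use PrEP". Counting age and education separately and including treatment arm gives about 14. First-line arm makes 15 for the non-responder tool. That is 58/15 ≈ 3.9 adherent women per predictor.
- Signal strength: not in the documents, so it was varied (population AUC 0.50 to 0.80).

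**Formulas**
- Penalized fit: maximize log-likelihood − ½ λ Σ s_j² β_j², with s_j the standard deviation of predictor j.
- Penalty: λ on 0-100 by corrected AIC (assumed to be the software default).
- Corrected slope: 1 − mean over resamples of (1 − slope_b) = mean of slope_b. Here slope_b is the slope of bootstrap model b on the original sample, and the training slope is taken as 1.
- True slope: slope of the final model in a simulated population of 20,000.

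**Base case** (175 women, 15 independent predictors, 33% adherent)

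| AUC | True slope, mean (median) | Penalty fixed, as coded | Fixed − mean true | Re-tuned in each resample | Re-tuned − mean true |
|---|---|---|---|---|---|
| 0.61 | 0.93 (0.91) | 1.91 | +0.98 | 1.17 | +0.24 |
| 0.66 | 1.27 (1.14) | 1.77 | +0.50 | 1.12 | −0.15 |
| 0.70 | 1.26 (1.13) | 1.50 | +0.24 | 1.05 | −0.21 |
| 0.74 | 1.16 (0.99) | 1.28 | +0.12 | 0.99 | −0.17 |
| 0.80 | 1.01 (0.94) | 1.07 | +0.06 | 0.91 | −0.10 |

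A second run at the same settings gave fixed-penalty means of 1.94, 1.68, 1.35 and 1.14 at AUC 0.61, 0.67, 0.71 and 0.76, against median true slopes of 0.94, 0.96, 0.92 and 0.86. Re-tuning lowered the median absolute error in all nine scenarios of that run (for example 0.96 to 0.35, and 0.58 to 0.27).

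**Sensitivity** (fixed-penalty mean against mean true slope)
- SAP template, 200 observations, 3 predictors: 1.02 against 1.02.
- 10 predictors: 1.54 against 1.40 (AUC 0.66); 1.14 against 1.12 (0.74); 1.01 against 0.99 (0.80).
- 20 predictors: 1.94 against 1.15 (0.66); 1.50 against 1.25 (0.74).
- 184 women, 40% adherent, 15 predictors: 1.61 against 1.23 (0.66); 1.19 against 1.08 (0.74).
- 150 women, 20% adherent, 15 predictors: 2.38 against 1.40 (0.66); 1.73 against 1.45 (0.74).
- Predictors correlated at 0.3, training slope still taken as 1: 1.91 against 0.98 (AUC about 0.62); 1.66 against 1.14 (0.67).
- Almost no signal (AUC 0.50-0.56): about 1.85 against 0 to 0.3; re-tuned about 1.19.
- Baseline tool, 350 women, 14 predictors: 1.25 against 1.13 (0.66); 1.04 against 1.02 (0.74).

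**Grid limit.** With 175 women and 15 predictors, the selected penalty sat at 100 in 41% of datasets at AUC 0.63 and in 77% at AUC 0.56, but in only 1% at AUC 0.74.

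**AUC.** The corrected AUC changed by less than 0.01 between the two procedures.

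**The case against.** The size is driven by assumptions. The documents fix neither the signal, nor the number of model terms, nor the event rate, and the SAP's own example shows no bias. This stands, so the figures can only be conditional.

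The code is an example on simulated data, and the text specifies Poisson regression without a penalty. If the analysts follow the text, the point does not arise. That stands as a condition. But the block is labelled as the code for fitting and assessing these models, so its order of steps is the only procedure on record. The Poisson-logistic mismatch is a separate matter.

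The R package could not be run. The fixed penalty in resampling, the corrected-AIC default and a training slope of 1 are assumptions. If the training slope is re-estimated, the bias is smaller: in a weak-signal case with 150 women, 18 predictors and 30% adherent, the fixed-penalty figure falls from 2.18 to 1.89 against a true 1.03. With correlated predictors or stronger signal it largely disappears. This also stands.

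The remedy is imperfect. Against the mean true slope, re-tuning at AUC 0.70 or above errs by about as much in the other direction (+0.24 against −0.21 at 0.70). Against the median true slope it is closer throughout. It stays near 1.2 with almost no signal and does not follow an individual model's slope.

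A reader might go further and infer that the code itself yields a slope of 1.4-2.2 for a tool whose true slope is 1, or that users will stretch its predictions. The documents support neither. The range needs weak-to-moderate signal and about 15 or more predictors. The true slope is about 1 only on average (10th-90th percentile about 0.6-2.1 at AUC 0.66). No section says the slope will be used to recalibrate.

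**Conclusion.** The omission is plain from the code: the penalty search is outside the bootstrap, so the promised correction is incomplete and the reported slope tends upward. For the non-responder tool, with about 175 women, about 15 predictors, about 33% adherent and the coded logistic model, the mean corrected slope is about 1.35-1.9 at AUC 0.61-0.71 against a median true slope of about 0.9-1.15. At AUC 0.74-0.80 the excess over the mean true slope falls to 0.06-0.12 with 15 predictors and about 0.02 with 10. In the 350-woman baseline tool at AUC 0.66 the corrected slope is about 1.2-1.25 against a mean true slope of about 1.1.

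All of this rests on the software keeping the penalty fixed and taking the training slope as 1. It is a minor point about one measure in a secondary analysis, worth correcting because the correction is cheap. Running the SAP's example would not reveal it.

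**What to change.** In SAP Secondary Analysis 2, repeat `pentrace()` inside each bootstrap sample. Apply each re-tuned model to the original sample, and compute the corrected slope and intercept from those results. Extend the penalty grid beyond 100, and report whether the chosen penalty lies at the limit.

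The cost is about ten lines of R and a longer run time, with no new data. State in the SAP that the corrected slope is an average property of the procedure, not an estimate of the final model's own slope, and that it is uninformative when the AUC is close to 0.5.
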